9.9 Definition of End of Study

The end of study will be the date of the last visit of the last patient at follow-up, at which point all of the study data has been entered and queries resolved. We anticipate that this will be by December 2021.

10 SAFETY REPORTING

Patients will not be placed at any additional risk during this study.

The participants in the 'simulation-training sub-group' of this study will be expected to participate in low-risk simulated surgical activities within the OOSEC. The low risk to participants will also be highlighted as part of the informed consent process, which will take place before any study-specific procedures or training are performed. Such activities will be those normally encountered in their training, such as the use of orthopaedic power tools, saws, and sharp instruments. As part of the baseline visit, the lead investigator, or suitably qualified deputy, will outline the materials and tasks involved in each training session to the participants. The training sessions will be delivered in a supervised setting to StR's within the OOSEC, which is part of the University of Oxford's premises (NDORMs). As specified previously the OOSEC is a secure enclosed laboratory space, which contains all the necessary equipment required to run the simulation-based and cognitive learning training.

In the unlikely event that any participant sustains an injury, we will follow the OOSEC safety policy. Any significant incidents will be recorded in a logbook within the OOSEC, and reported directly to the Health & Safety Manager within the Medical Sciences Division of the University of Oxford.

10.4 Definition of Serious Adverse Events

A serious adverse event is any untoward medical occurrence that:

- results in death
- is life-threatening
- requires inpatient hospitalisation or prolongation of existing hospitalisation

- results in persistent or significant disability/incapacity
- consists of a congenital anomaly or birth defect.

As outlined in section 10 above, we do not anticipate any serious adverse events whilst conducting our intervention simulation training. In the extra-ordinary event that any were to occur we would follow the OOSEC Health & Safety Policy.

This study does not add any additions to the usual inherent risks associated with THR surgery. If any patient were to experience a serious adverse event during the operation, peri- or post-operative period, these would be as a consequence of their normal care, and not this study. These would therefore be investigated in line with NHS protocols. We will also report on patient's peri-operative morbidity (30 day) as part of the secondary objectives outlined in section 6 of this study.

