6. OBJECTIVES AND OUTCOME MEASURES

Objectives	Outcome Measures	Timepoints of evaluation
Primary To assess the impact of simulation training on surgical trainee performance and patient outcomes following THR.	Participants: 
 Wireless motion data metrics from elbow worn sensors (hand movements, path length and time taken) Global Rating Scales (GRS). Objective Structured Assessment of Technical Skills (OSATS). Surgical checklists. Patients: 
 X-ray analysis of THR.[4] Blood loss and transfusion rates. Peri-operative patient morbidity In-patient length of stay. PROMs: EQ-5D and OHS. 	Intra-operative assessments to be performed at a minimum of 8 separate THR operations for each participant in Group 1 (StR'S) over a 6-month period. Outcome measures data will be collected for all patients who have had a THR performed by any participant as the lead surgeon in this study.
Secondary To define an expert standard when performing a primary elective THR. To determine if operative surgeon performance metrics during a THR relate to surgical experience, or patient outcomes.	Participants: 
 Wireless motion data metrics from elbow worn sensors (hand movements, path length and time taken) Patients: 
 X-ray analysis of THR.[4] Blood loss and transfusion rates. Peri-operative patient morbidity In-patient length of stay. PROMs: EQ-5D and OHS. 	Intra-operative assessments at a minimum of 5 separate THR operations for each participant in Group 2 (Experts & Fellows). Outcome measures data will be collected for all patients who have had a THR performed by any participant as the lead surgeon.

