9.7 Intra-operative surgeon performance data collection

The following protocol will apply to all episodes of intra-operative performance data collection for StR's and Fellows. The intra-operative data collection for Consultant performed operations will differ slightly in that they require no supervision, and no surgeon will 'take over' the operation. However, the methods for recording the intra-operative data will remain the same.

A maximum of two study participants (excluding Consultants) will attend any given list. The PI ([name]) will attend the World Health Organisation (WHO) briefing in theatre on the morning of the list, introduce themselves and explain their role during the list. If recording an StR, neither the participant or PI will disclose which arm of the study the participants are in (routine training, or additional simulation training). The supervising Consultant will confirm the cases on the list the StR or AF's will be performing under supervision and training.

Operative protocol

After anaesthesia and patient set-up, the supervising Consultant and participant will scrub in up in the usual manner with the motion sensors in position on the lead surgeon's elbows under their sterile gown (see Appendix C). The procedure will then continue routinely and normally, but with the PI collecting motion data via the wireless Bluetooth sensors. The PI will also manually record the timings of each stage of the THR operation. This process will allow synchronisation of motion data to the participants progression throughout the stages of the operation. Data collection will stop when the dressing has been applied to the surgical wound.

Following completion of the operation, the participants in conjunction with the supervising Consultant will be asked to complete short written assessments of the lead surgeons' intra-operative performance. These assessments may include: Global Rating Scales (GRS), Objective Structured Assessment of Technical Skills (OSATS), and surgical checklists.

Intra-operative deviations or interruptions

Sometimes the supervising Consultant needs to take over part or all of an operation if it proves particularly difficult. In the event that a procedure has to be taken over completely by the Consultant then data recording will stop. If minor adjustments only are made by the Consultant during the operation then these will be noted and time marked against the motion data.

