10.5 Reporting Procedures for Serious Adverse Events

A serious adverse event occurring to a participant will be reported to the REC that gave a favourable opinion of the study where in the opinion of the Chief Investigator the event was 'related' (resulted from administration of any of the research procedures), and 'unexpected' in relation to those procedures. Reports of related and unexpected SAEs will be submitted within 15 working days of the Chief Investigator becoming aware of the event, using the HRA report of serious adverse event form (see HRA website).

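### Section 10.4 attributes every patient SAE to normal care in advance, so on either reading of 'participant' in 10.5 no patient event is assured a case-level relatedness assessment

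*Combined protocol and SAP*

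**What the plan says.** Section 10 opens with "Patients will not be placed at any additional risk during this study". Section 10.4 repeats the assurance for the operation itself: "This study does not add any additions to the usual inherent risks associated with THR surgery". It then takes any patient SAE during or after surgery and states that "these would be as a consequence of their normal care, and not this study". The next sentence draws the consequence: "These would therefore be investigated in line with NHS protocols". Section 10.4 adds that 30-day peri-operative morbidity will be reported as an outcome.

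Section 10.5 sets the study's reporting rule: "A serious adverse event occurring to a participant will be reported to the REC". The condition is "where in the opinion of the Chief Investigator the event was 'related' (resulted from administration of any of the research procedures", and the event must also be unexpected. The time limit is 15 working days from the Chief Investigator becoming aware.

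Two other places bear on this. The primary objective in section 6 is "To assess the impact of simulation training on surgical trainee performance and patient outcomes following THR", with peri-operative morbidity among its listed outcomes. Section 9.7 describes the operation going ahead with sensors on the lead surgeon's elbows under the sterile gown, "with the PI collecting motion data via the wireless Bluetooth sensors", and with the PI timing each stage.

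**The concern.** Whether an adverse event is related to the research is normally judged after the event, by a named person looking at that case. Section 10.5 is written that way. Section 10.4 gives the answer for all patients before any event has happened, and the word 'therefore' makes the NHS-only routing rest on that answer. This is a stated rule, not a missing detail.

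What is at stake is limited but real. If a research procedure in theatre did contribute to a patient's event, nothing in the text brings that event to the Chief Investigator, and so nothing brings it to the REC as a related SAE. Section 13.5 marks study monitoring as not applicable, and section 13.6 provides no oversight committee.

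**Working it through.** The documents state no SAE rate and no expected number of SAEs, so there is no figure of theirs to reproduce. The check is mainly a comparison of sections, followed by simple arithmetic for size.

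**Step 1: who is a 'participant' in 10.5?** The usage conflicts.
- The synopsis (section 3) calls patients 'Patient Participants'.
- Section 9.8 speaks of a participant or a patient as alternatives, and section 12 also lists the two separately.
- Section 10.5 does not define the word.

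**Step 2: follow each reading through.**

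| Reading of 'participant' in 10.5 | Effect on a patient SAE |
|---|---|
| Includes patients | 10.5 asks for the Chief Investigator's opinion; 10.4 has already answered that the event is not due to the study |
| Surgeons only | 10.5 does not apply; 10.4 sends the event to NHS investigation alone |

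Under both readings, 10.5 still works for surgeons. Under neither does the text provide a step that brings a patient SAE to the Chief Investigator for a judgement on relatedness.

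**Step 3: are there research procedures to which a patient event could be related?** Yes. Section 9.7 places sensor wear, wireless data capture and stage timing within the patient's operation. Any added risk may be negligible, but 10.5 leaves that question to case assessment.

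**Step 4: does the rest of the plan treat patient harm as a possible study effect?** Section 6 lists peri-operative morbidity under the primary objective, and section 11 tests it between groups. Section 11 also has reviewers grade post-operative X-rays, with a top category for concerns that require revision surgery. A revision needing admission would meet the hospitalisation limb of the 10.4 definition, so a study assessment could itself identify an SAE that 10.4 has already attributed elsewhere.

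**Step 5: size.** Inputs: 12 to 16 registrars and 6 to 8 fellows (section 8.1); 5 consultants; 8 patients per registrar and 5 per fellow or consultant (section 3).
- Lower: 12 × 8 + 6 × 5 + 5 × 5 = 96 + 30 + 25 = 151 patients.
- Upper: 16 × 8 + 8 × 5 + 5 × 5 = 128 + 40 + 25 = 193 patients, which matches the synopsis.
- Assumed SAE rate of 2 to 5% (not from the documents): 151 × 0.02 = 3.0 at the low end and 193 × 0.05 = 9.7 at the high end, so about 3 to 10 events.

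**The case against.** The best case for the plan is that this is a surgeon-training study with no departure from routine patient care (section 7). Section 5 says earlier projects established the safety of the sensors, and 'related' in 10.5 is confined to research procedures. Almost every patient SAE would be an ordinary surgical event that a case review would also call unrelated. That stands, and it keeps the expected yield of any review very small. It does not justify fixing the answer beforehand.

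A reader might also infer more than the text supports:

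- *That 10.4 removes the Chief Investigator's judgement.* It does not. The clause in 10.5 is not withdrawn and still governs surgeons. If 10.5 never covered patients, there was nothing to remove. For patients, 'pre-empts or leaves uncovered' is as far as the text goes.
- *That 10.4 contradicts the trial's premise.* The protocol asks whether training affects patient outcomes and hopes for improvement; it does not assume an effect. The advance attribution is awkward beside that question, but it does not contradict a stated fact. A group difference in morbidity is also a trial result, not a case-level finding of relatedness.
- *That this rule is the only safety check on patients and can detect nothing.* Patient SAEs are investigated under NHS protocols (10.4). Registrars operate under a consultant who can take over (9.7). Thirty-day morbidity is collected and compared, and X-rays are graded by blinded reviewers (11, 12). Suspected serious breaches go to the sponsor within 1 working day (15), progress reports go to the REC annually (16.8), and section 13 allows monitoring or audit. None of these gives a case-level relatedness assessment, but they are not nothing.
- *That the sensors are a hazard in the operative field.* Section 9.7 puts them on the elbows, under the gown.

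A fair objection to the obvious remedy is that asking whether one patient's event was related to simulation training could reveal the surgeon's arm. Section 9.7 keeps the arm undisclosed in theatre and section 9.5 blinds the assessors. The question can also rarely be answered for a single case. The objection stands, and the fix is limited accordingly.

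**Conclusion.** The concern holds in a limited form. The text decides relatedness for all patient SAEs by declaration, and the undefined 'participant' in 10.5 means that neither reading repairs this. About 3 to 10 events would go without a study-level relatedness assessment. That range rests on full delivery of 151 to 193 patients and on an SAE rate that is assumed, not documented. It counts all SAEs, not those caused by a research procedure; the latter number cannot be estimated from the documents and is probably very small. The likely harm is therefore low. The change should still be made, because the wording settles a patient-safety question in advance and is cheap to correct.

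**What to change.** 1. In 10.4, delete the sentence that attributes patient SAEs to normal care in advance, together with the 'therefore' that depends on it. Keep NHS investigation exactly as it is.
2. Qualify the opening sentence of section 10 so that it no longer states the absence of patient risk as a certainty.
3. In 10.5, define 'participant' to include enrolled patients as well as surgeons.
4. Add one step: when the existing record review (section 12) finds a patient event meeting the 10.4 definition, the PI passes it to the Chief Investigator. The Chief Investigator records, without reference to the surgeon's allocation, whether it resulted from a research procedure in theatre (sensors, data capture).
5. Leave any effect of simulation training on patient harm to the between-group morbidity comparison in section 11.

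Only related and unexpected events then go to the REC, on the existing 15-working-day timeline. The cost is a few sentences in section 10 and a short relatedness entry for a handful of events. It needs no new staff, visits or patient data.

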10.5 Reporting Procedures for Serious Adverse Events

A serious adverse event occurring to a participant will be reported to the REC that gave a favourable opinion of the study where in the opinion of the Chief Investigator the event was 'related' (resulted from administration of any of the research procedures), and 'unexpected' in relation to those procedures. Reports of related and unexpected SAEs will be submitted within 15 working days of the Chief Investigator becoming aware of the event, using the HRA report of serious adverse event form (see HRA website).

11 STATISTICS AND ANALYSIS

Analysis of motion data.

Motion data from the wireless sensors produces performance surrogate markers such as: the number of movements (major & minor); total path length; and smoothness/economy of movement. Data distributions will be assessed for normality using the Shapiro-Wilk test. Previous studies show such data are not normally distributed, and we would expect to use non-parametric tests, such as the Mann-Whitney U test to compare the performance metrics between the 2 groups of participants (StR's against Experts & Fellows). The Mann-Whitney U test will also be used to compare performance metrics between the two sub-groups of StR's (control and intervention), and also within the intervention sub-group in order to compare performance before and after training.

Performance metrics within all groups of participants will be reported using descriptive statistics to outline the central tendency (mean, median, and mode) and variation (range, variance, and standard deviation) in readings obtained. The Kruskal-Wallis one-way analysis of variance (ANOVA) test will be used to test for differences in the mean values obtained for all performance metrics between the two groups of participants. The Wilcoxon signed-rank test will be used to determine any differences in performance metric between the two groups.

Analysis of other routinely obtained data

X-ray (radiograph) analysis:

X-rays will be reviewed by two independent Consultant Orthopaedic Surgeons who will be blinded to the patient and lead surgeon's identity in order to reduce bias. There are several important parameters to be evaluated when reviewing a pelvic x-ray, therefore we will ask each reviewer to allocate a categorical global rating (see below) for both the pre- and post-operative x-rays. [5] The Chi-squared test will be used

to determine if there are any significant differences between each group, and also intra-group differences (for example StR's before and after additional training).

Pre-operative x-ray

- 1: Hip osteoarthritis without significant bone loss.
- 2a: Hip osteoarthritis with significant bone loss on acetabular side.
- 2b: Hip osteoarthritis with significant bone loss on femoral side.
- 3: Hip osteoarthritis with significant bone loss on both acetabular and femoral sides.

Post-operative x-ray

- 1: Excellent implant position and restoration of hip anatomy.
- 2a): Good overall with minor imperfections on acetabular side.
- 2b): Good overall with minor imperfections on femoral side.
- 3: Moderate concerns but does not require revision surgery.
- 4: Significant concerns requiring revision surgery.

Every patients post-operative x-ray will also be reviewed by the PI ([name]) for acetabular component positioning (inclination and version) using the methodology described by Bachhal [4]. This continuous data will be assessed for normality of distribution, and analysed using similar methodology as described above for the motion data. We will be looking for any statistically significant differences between the 2 groups of participants, within the two sub-groups of StR's (control and intervention), and also within the intervention sub-group in order to compare performance before and after additional training.

Other outcomes data:

Following collection of the outcome measures listed below, the normality of the data distribution will be checked with the Shapiro-Wilk test. Descriptive statistics will be used to outline the central tendency and variation of these data sets. Statistical analyses between each group of participants will be performed using either the parametric unpaired t-test or a non-parametric Mann-Whitney U test depending on the distribution of the data. Subsequent analysis of the outcomes data using a paired t-test, or Mann-Whitney U test will also be performed within the two sub-groups of the StR's (control and intervention), and also within the intervention sub-group in order to compare outcomes before and after additional training.

- Theatre time usage.
- Blood loss (pre-/post-op haemoglobin levels)
- In-patient length of stay.
- PROMs: EQ-5D and OHS.

The Chi-squared test (or Fishers exact test if the sample is <5) will be used to determine any significant differences between the groups regarding the incidence of blood transfusions or peri-operative morbidity.

All of these tests will be performed using the SPSS statistical package, which is available for any registered student on the University of Oxford current Licencing agreement.

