7. STUDY DESIGN

Please see Appendix A for study flow diagram.

This is a prospective randomised controlled study designed to assess the impact of specific training interventions on surgical trainee's operative performance and patient outcomes following primary elective THR. We will also study the performance and patient outcomes of both 'Experts' and 'Fellows' in an additional comparator group, which will allow a potential expert standard in THR to be defined.

All study participants will be recruited from 2 Hospitals within the Thames Valley (Oxford) Post-graduate Medical Deanery, and will be composed of: Trauma & Orthopaedic Specialty Registrars ('StRs') holding national training numbers; Consultant Orthopaedic Surgeons ('Experts'); and Orthopaedic Arthroplasty Fellows ('Fellows'). Over the 18-24 month anticipated study period we aim on recruiting a total of up to 16 StR's, 8 Fellows, and 5 Experts. See section 9 for further details on participant recruitment.

StR's will be randomised in a 1:1 ratio to receive either: routine normal Deanery training (the control group, n=8); or routine normal Deanery training with additional simulation-based and cognitive learning (the intervention group, n=8). The intervention group will receive this training for 1-2 hours per week over a 4 to 6-week period. The 'Experts' and 'Fellows' will not be eligible for any intervention, and will act as a separate comparator group.

All participants will be assessed intra-operatively at set timepoints when performing elective primary THR surgery on patients within the named NHS Hospitals. The timepoints will vary depending upon each group. Each StR enrolled into this study will be assessed at a minimum of 8 separate THR operations over a 6-month period, commencing at 6 weeks in to their 6-month clinical placement. Both the 'Fellows' and 'Experts' will be assessed at a minimum of 5 separate THR operations depending upon the reliability of their performance data.

All patients in this study will have been listed for routine elective primary THR surgery under a named Orthopaedic Consultant on the NHS. There will be no interventions or deviations from routine clinical practise regarding the pre-operative investigations or work-up, the operation itself, the peri-operative care, or post-discharge follow-up.

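### Registrars are randomised, but section 11 states no unit of analysis: its categorical tests ignore clustering by surgeon as written, and its other comparisons leave the unit open

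*Combined protocol and SAP*

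**What the plan says.** Section 7 randomises registrars 1:1, 8 per arm; section 9.4 expects 6-8 per arm, spread evenly over two hospitals. On repeated measurement, section 7 says "Each StR enrolled into this study will be assessed at a minimum of 8 separate THR operations". The synopsis plans 8 patients per registrar (128 in all), and section 6 collects outcomes for every patient of a participating lead surgeon, so 8 is a floor.

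Section 11 then assigns tests:

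- Motion metrics, control v intervention: "The Mann-Whitney U test will also be used to compare performance metrics between the two sub-groups of StR's (control and intervention". Cup angles follow similar methods.
- Motion metrics, Trainee v Expert/Fellow: Mann-Whitney, plus a Kruskal-Wallis test for "differences in the mean values obtained for all performance metrics between the two groups of participants" and a Wilcoxon signed-rank test, also between the two groups.
- X-ray grade: "we will ask each reviewer to allocate a categorical global rating", with a chi-squared test for "any significant differences between each group, and also intra-group differences".
- Theatre time, haemoglobin, length of stay and PROMs: unpaired t or Mann-Whitney between groups, then "Subsequent analysis of the outcomes data using a paired t-test, or Mann-Whitney U test will also be performed within the two sub-groups".
- Transfusion and morbidity: "The Chi-squared test (or Fishers exact test if the sample is <5) will be used to determine any significant differences between the groups".

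GRS, OSATS and checklists, listed under the primary objective in section 6, are not named in section 11. Nowhere does the section say whether one observation is a surgeon, an operation, a patient or a rating. It defines no per-surgeon summary and names no clustered method.

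**The concern.** Eight operations by one registrar are not eight independent pieces of evidence about training. If outcomes correlate within surgeon and the rows are pooled, the standard error is too small. A chance difference between two sets of 6-8 trainees can then be reported as an effect of simulation. Most of the affected outcomes sit under the primary objective in section 6, and section 5 intends the results to inform recommendations on national training.

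The tests named assume either independent observations or simple pairs. A paired t-test or signed-rank test handles one pair per subject, not eight or more operations per registrar. The same text also permits an 8 v 8 or a 64 v 64 analysis, with very different p-values, and nothing stops that choice being made after the data are seen.

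**Working it through.** **Inputs from the protocol.** k = 8 registrars per arm (section 7), or 6 (section 9.4); m = 8 observations per registrar (synopsis, section 7); 8 Fellows and 5 Consultants with 5 patients each (synopsis).

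**Inputs assumed.** Two-sided 5%, and an ICC range of 0.02 to 0.5. The documents give neither.

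**The plan's own figure.** 16×8 + 8×5 + 5×5 = 128 + 40 + 25 = 193, as stated. This is a count of patients, not a power calculation.

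**Categorical outcomes: reading the text.** An incidence compared by chi-squared or Fisher needs counts of patients. A chi-squared table of X-ray grades needs patients or single ratings as rows. Either way the surgeon drops out. I assume that the groups mentioned include control v intervention, since no other categorical test is named.

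**Continuous outcomes if rows were pooled.** Design effect DE = 1 + (m−1)×ICC = 1 + 7×ICC. Effective number per arm = 64/DE. True size ≈ 2×[1 − Φ(1.96/√DE)]. The last column is the range over repeated simulations of the Mann-Whitney test (normal data, no treatment effect).

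| ICC | DE | Effective n per arm | Size, formula | Size, simulated |
|---|---|---|---|---|
| 0.02 | 1.14 | 56 | 6.6% | 6.7-6.9% |
| 0.05 | 1.35 | 47 | 9.2% | 8.8-9.2% |
| 0.1 | 1.70 | 38 | 13.3% | 12.6-13.9% |
| 0.3 | 3.10 | 21 | 26.6% | 26.3-26.6% |
| 0.5 | 4.50 | 14 | 35.6% | 35.1-36.0% |

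Six registrars per arm give nearly the same sizes (8.9% at ICC 0.05, about 36% at 0.5). With 16 operations per registrar, the simulated size is about 14% at ICC 0.05 and 21% at 0.1. Trainee v Expert/Fellow, pooled as 16×8 v 13×5, gives 8%, 11%, 21% and 29% at ICC 0.05, 0.1, 0.3 and 0.5.

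**Transfusion and morbidity.** Beta-binomial simulation, 64 v 64, with the small-sample rule read as an expected count below 5 (in brackets: an observed cell below 5). The incidences are assumed.

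| Incidence | ICC 0.05 | ICC 0.1 | ICC 0.3 |
|---|---|---|---|
| 5% | 4% (3%) | 7% (5%) | 16% (14%) |
| 20% | 9% (9%) | 13% (13%) | 27% (27%) |

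**X-ray grade, one row per patient.** With an assumed split of 40/20/20/15/5% over the five grades, the size is 6%, 8% and 18% at the same ICCs.

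**Surgeon as unit.** An exact Mann-Whitney test on one summary per registrar has enumerated size 4.99% (8 v 8) or 4.11% (6 v 6), whatever the ICC.

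**The case against.** The strongest defence is that section 11 may already intend one value per surgeon. It compares groups of participants, and in sections 3 and 6 the participants are surgeons. It speaks of mean values obtained. Section 7 assesses Fellows and Experts "at a minimum of 5 separate THR operations depending upon the reliability of their performance data", which fits averaging within a surgeon. On that reading the Mann-Whitney comparison of arms is valid. This stands for the continuous outcomes. A reader might infer that the plan pools operations, or that none of its tests could be right; the documents support neither. What remains is that no such value is defined: not mean or median, and not which operations count.

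Second, the harm is least documented where the text is clearest. Nothing in the documents bears on the ICC of patient outcomes. Section 5 reports that motion metrics separated surgeons by training level in earlier work, and section 8.1 sets no limit on training year. That makes a non-zero ICC plausible for motion metrics but gives no size. This stands too. The 26-35% figures need an ICC of 0.3-0.5 and should not be read as the trial's expected error rate.

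Third, a reader might infer that the two X-ray reviewers' ratings will be entered as separate rows. The text does not say so, and that would be double counting, a separate matter from clustering by surgeon. It carries no weight here beyond the need for a rule to combine the ratings.

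Finally, morbidity is placed under the secondary objectives in section 10.4, although section 6 lists it under both.

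**Conclusion.** The point holds in two parts. The chi-squared and Fisher tests of transfusion, morbidity and X-ray grade are wrong as written for a comparison of randomised registrars. For motion metrics, GRS, OSATS, checklists, cup angles, theatre time, haemoglobin, length of stay and PROMs, the unit is unspecified rather than wrong.

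The size depends on an ICC that the documents do not give. With 8 observations per registrar, inflation is small at ICC 0.02 or below and, for a 5% incidence, up to about ICC 0.1. It would be going too far to infer that rare events are always safe: at ICC 0.3 the 5% incidence case reaches 16%. At ICC 0.1 or above, pooled continuous outcomes and 20% incidences have error rates of at least about 13%.

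Confidence is high in the omission and only conditional in its effect. It should be settled before any outcome data are compared, because the choice of unit cannot be made credibly afterwards.

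**What to change.** Amend section 11 as follows:

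1. State the significance level, and that the surgeon is the unit of inference.
2. Reduce each outcome to one prespecified summary per registrar. Name one summary for each continuous outcome, including GRS, OSATS and checklists, and say which operations count. Use a proportion for transfusion and for morbidity. For X-ray grade, combine the two reviewers into one rating per film, then name one registrar-level summary.
3. Compare arms with an exact rank or permutation test on these summaries, stratified by hospital if allocation is balanced by site as section 9.4 plans. Ignoring a balanced site factor keeps the test valid but conservative: simulated size is about 4.3%, 3% and 0.6% for assumed site differences of 0.5, 1 and 2 SDs of a registrar mean.
4. For continuous outcomes, a mixed model with a random surgeon intercept and a small-sample correction is an alternative, on a suitable scale because section 11 expects non-normal motion data.
5. Use surgeon-level summaries for Trainee v Expert/Fellow. For any within-group comparison, use one before/after pair per registrar and a paired test.

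**Cost.** Wording and some advance decisions; no extra data and no change to randomisation. A permutation test may need software other than SPSS (not checked).

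Apparent precision falls. The SD of a registrar mean is √(ICC + (1−ICC)/8), in SDs of a single operation. For 80% power with normal data, the exact Mann-Whitney test needs a difference of 1.555 of these (8 v 8): 1.555×0.411 = 0.64 SD at ICC 0.05, rising to 1.555×0.75 = 1.17 SD at ICC 0.5. Treating 64 v 64 operations as independent would suggest 0.50 SD. With 6 v 6 the range is 0.79-1.44 SD. These figures take no account of site differences.

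For rare binary outcomes the permutation test is conservative (size 0.1-3%) and weak: power for 5% v 15% is 28% at ICC 0.02 and 19% at 0.1 (8 v 8), or 16% and 11% (6 v 6). A null result on transfusion or morbidity should not be read as no effect.
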